2. INTRODUCTION

This SAP provides the detailed methodology for summary and statistical analyses of the data collected in Study C3671006. This document may modify the plans outlined in the protocol; however, any major modifications of the primary endpoint definition or its analysis will also be reflected in a protocol amendment.

2.1. Study Objectives, Endpoints, and Estimands

The estimands corresponding to each primary, secondary, and exploratory objective are described in Table 2.

Table 2. Study Objectives, Endpoints, and Estimands

Objectives	Endpoints	Estimands
Primary Safety:	Primary Safety:	Primary Safety:
To evaluate the safety profiles of RSVpreF when coadministered with SIIV (RSVpreF + SIIV) or administered 1 month after SIIV.	
 Local reactions (redness, swelling, and pain at the injection site) self-reported on e-diaries for 7 days after vaccination. Systemic events (fever, fatigue, headache, nausea, vomiting, diarrhea, muscle pain, and joint pain) self-reported on e-diaries for 7 days after vaccination. AEs. SAEs. 	
In participants receiving at least 1 dose of study intervention (RSVpreF, placebo, or SIIV) and having safety follow-up after vaccination in each vaccine group:
 
 The percentage of participants reporting prompted local reactions within 7 days after vaccination with RSVpreF or placebo. The percentage of participants reporting prompted systemic events within 7 days after vaccination with RSVpreF or placebo.

Table 2. Study Objectives, Endpoints, and Estimands

Objectives	Endpoints	Estimands
		
 The percentage of participants reporting AEs within 1 month after each vaccination. The percentage of participants reporting SAEs within 1 month after each vaccination.
Primary RSV Immunogenicity		

To demonstrate that the immune responses elicited by RSVpreF when coadministered with SIIV (RSVpreF + SIIV) are noninferior to those elicited by RSVpreF alone when administered 1 month after SIIV.
	
 RSV A and RSV B NTs. 	
In participants in compliance with the key protocol criteria (evaluable participants):
 
 GMR of NTs at 1 month after vaccination with RSVpreF for each RSV subfamily (A or B) in the coadministration group (RSVpreF + SIIV) to the sequential-administration group (RSVpreF alone).
Primary SIIV Immunogenicity		

To demonstrate that the immune responses elicited by SIIV when coadministered with RSVpreF (RSVpreF + SIIV) are noninferior to those elicited by SIIV alone.
	
 Strain-specific HAI titers. H3N2-neutralizing antibody titers (if interpretable H3N2-HAI titers cannot be obtained). 	
In participants in compliance with the key protocol criteria (evaluable participants):
 
 GMR of the strain-specific HAI (or H3N2-neutralizing antibody) titers 1 month after vaccination with SIIV in the coadministration group (RSVpreF + SIIV) to the sequential-administration group (SIIV alone).

[figure not shown]

Table 2. Study Objectives, Endpoints, and Estimands

Objectives	Endpoints	Estimands
Secondary RSV Immunogenicity		
To describe immune responses elicited by RSVpreF when coadministered with SIIV or when administered alone	
 RSV A and RSV B NTs. 	In participants in compliance with the key protocol criteria (evaluable participants) from each vaccine group: 
 Geometric mean of the NTs for RSV A and RSV B before vaccination and at each applicable visit after vaccination with RSVpreF. GMFR of the NTs for RSV A and RSV B from before vaccination to each applicable visit after vaccination with RSVpreF.
Secondary SIIV Immunogenicity		
To describe immune response elicited by SIIV when coadministered with RSVpreF or when administered alone.	
 Strain-specific HAI titers. H3N2-neutralizing antibody titers (if interpretable H3N2-HAI titers cannot be obtained). 	In participants in compliance with the key protocol criteria (evaluable participants) from each vaccine group: 
 GMTs before vaccination and 1 month after vaccination with SIIV. GMFR of strain-specific HAI titers (or H3N2-neutralizing antibody titers if interpretable H3N2-HAI titers cannot be obtained) from before vaccination to 1 month after vaccination with SIIV.
CCI		
Exploratory SIIV Immunogenicity:		
To further describe immune responses elicited by SIIV when coadministered with RSVpreF or when administered alone.	
 Strain-specific HAI titers H3N2-neutralizing antibody titers (if interpretable H3N2-HAI titers cannot be obtained). 	N/A

2.1.1. Primary Estimand(s)

2.1.1.1. Primary RSV Immunogenicity Estimands

The primary estimands for the RSV immunogenicity objective will use the hypothetical strategy and compare the RSVpreF immune response in participants without the intercurrent events. In other words, the immune response is estimated in the hypothetical setting where participants follow the study schedule and protocol requirements as directed. It includes the following 5 attributes:

- **Treatment condition:** RSVpreF administered at Visit 1 in the coadministration group vs RSVpreF administered at the Month 1 visit (Visit 2) in the sequential-administration group.
- **Population:** Older adults, as defined by the study inclusion and exclusion criteria.
- **Variables:** RSV serum NTs for subgroup A and subgroup B measured at the Month 1 visit in the coadministration group and RSV NTs for subgroup A and subgroup B measured at the Month 2 visit for the sequential-administration group.
- **Intercurrent events:** The following intercurrent events could impact the interpretation or the measurement of the immune response:
 1. The participant did not receive the study intervention as randomized.
 2. The participant did not meet the study inclusion criteria or did meet the exclusion criteria.
 3. Major protocol violations: The participant received a prohibited vaccine or treatment that may alter the immune response.
 4. Blood was taken outside an acceptable window for immunogenicity evaluation (<25 days after RSVpreF administration or >49 days after RSVpreF administration).

The clinical question of interest is based on whether the immune response elicited from RSVpreF via coadministration with SIIV, without any influence from any other immune-modifying drugs or vaccines and measured at a homogeneous time window, is noninferior to that of RSVpreF administered alone (ie, without SIIV). Therefore, all data after intercurrent events 1, 2, and 3, as well as all data at intercurrent event 4, if collected, will be excluded. Major protocol violations will be determined by clinical review (through the data handling memo).

- **Population-level summary:** GMR, defined as the ratio of RSV A and RSV B neutralizing GMTs between the 2 treatment groups.

2.1.1.2. Primary SIIV Immunogenicity Estimands

The primary estimands for the SIIV immunogenicity objective will use the hypothetical strategy and compare the SIIV immune response among participants without the intercurrent events. In other words, the immune response is estimated in the hypothetical setting where participants follow the study schedule and protocol requirements as directed. It includes the following 5 attributes:

- **Treatment condition:** SIIV administered in the coadministration group vs SIIV administered in the sequential-administration group at Visit 1.
- **Population:** Older adults, as defined by the study inclusion and exclusion criteria.
- **Variables:** Strain-specific HAI titers (or H3N2-neutralizing antibody titers if interpretable H3N2-HAI titers cannot be obtained) measured at the Month 1 visit (Visit 2).
- **Intercurrent events:** The following intercurrent events could impact the interpretation or the measurement of the immune response:
 1. The participant did not receive the study intervention as randomized.
 2. The participant did not meet the study inclusion criteria or did meet the exclusion criteria.
 3. Major protocol violations: The participant received a prohibited vaccine or treatment that may alter the immune response.
 4. Blood was taken outside an acceptable window for immunogenicity evaluation (<25 days or >49 days after SIIV administration).

The clinical question of interest is based on whether the immune response elicited from SIIV via coadministration with RSVpreF, without any influence from any other immune-modifying drugs or vaccines and measured at a homogeneous time window, are noninferior to that of SIIV administered alone (ie, without RSVpreF). Therefore, all data after intercurrent events 1, 2, and 3, as well as all data at intercurrent event 4, if collected, will be excluded. Major protocol violations will be determined by clinical review (through the data handling memo).

- **Population-level summary:** GMR, defined as the ratio of strain-specific HAI (or H3N2-neutralizing antibody titers if interpretable H3N2-HAI titers cannot be obtained) GMTs between the 2 treatment groups.

2.1.1.3. Primary Safety Estimands

The primary estimands for the safety objective will use the treatment policy strategy and estimate the safety rate regardless of whether an intercurrent event occurs.

Reactogenicity estimands after Vaccination 1 have the following 5 attributes:

- **Treatment condition**: RSVpreF or placebo administered at Visit 1.
- **Population**: Older adults, as defined by the study inclusion and exclusion criteria.
- **Variables**: Each prompted item from the e-diary from Days 1 through 7 after vaccination (refer to [Section 3.1.3.1](#), and [Section 3.1.3.3](#)).
- **Intercurrent events**: Some of the intercurrent events listed in [Section 2.1.1.1](#) and [Section 2.1.1.2](#) may apply. However, all data collected after the intercurrent event will be included.
- **Population-level summary**: The rates of reporting each prompted reactogenicity item in the RSVpreF group and the placebo group separately.

Reactogenicity estimands after Vaccination 2 have the following 5 attributes:

- **Treatment condition**: RSVpreF or placebo administered at the Month 1 visit (Visit 2).
- **Population**: Older adults, as defined by the study inclusion and exclusion criteria.
- **Variables**: Each prompted item from the e-diary from Days 1 through 7 after vaccination (refer to [Section 3.1.3.1](#), and [Section 3.1.3.3](#)).
- **Intercurrent events**: Some of the intercurrent events listed in [Section 2.1.1.1](#) and [Section 2.1.1.2](#) may apply. However, all data collected after the intercurrent event will be included.
- **Population-level summary**: The rates of reporting each prompted reactogenicity item in the RSVpreF group and the placebo group separately.

AE and SAE estimands after Vaccination 1 have the following 5 attributes:

- **Treatment condition**: RSVpreF or placebo administered at Visit 1.
- **Population**: Older adults, as defined by the study inclusion and exclusion criteria.

- **Variables:** AEs reported within 1 month after Vaccination 1 (before Vaccination 2), SAEs reported within 1 month after Vaccination 1 (before Vaccination 2) (refer to [Section 3.1.3.4](#) through [Section 3.1.3.5](#)).
- **Intercurrent events:** Some of the intercurrent events listed in [Section 2.1.1.1](#) and [Section 2.1.1.2](#) may apply. However, all data collected after the intercurrent event will be included.
- **Population-level summary:** The rates of reporting AEs and SAEs in the RSVpreF group and the placebo group separately.

AE and SAE estimands after Vaccination 2 have the following 5 attributes:

- **Treatment condition:** RSVpreF or placebo administered at the Month 1 visit (Visit 2).
- **Population:** Older adults, as defined by the study inclusion and exclusion criteria.
- **Variables:** AEs reported within 1 month after Vaccination 2 and SAEs reported within 1 month after Vaccination 2 (refer to [Section 3.1.3.4](#) through [Section 3.1.3.5](#)).
- **Intercurrent events:** Some of the intercurrent events listed in [Section 2.1.1.1](#) and [Section 2.1.1.2](#) may apply. However, all data collected after the intercurrent event will be included.
- **Population-level summary:** The rates of reporting AEs and SAEs in the RSVpreF group and the placebo group separately.

2.1.2. Secondary Estimand(s)

2.1.2.1. Secondary RSV Immunogenicity Estimands

The estimands for the secondary RSV immunogenicity objective will use the hypothetical strategy and estimate the RSVpreF immune response when the intercurrent event would not occur. In other words, the immune response is estimated in the hypothetical setting where participants follow the study schedule and protocol requirements as directed.

Estimands for the secondary RSV immunogenicity objective have the following 5 attributes:

- **Treatment condition:** RSVpreF administered at Visit 1 in the coadministration group and RSVpreF administered at the Month 1 visit (Visit 2) in the sequential-administration group.
- **Population:** Older adults, as defined by the study inclusion and exclusion criteria.

- **Variables:** RSV serum NTs for RSV A, RSV B, and RSV A and B combined (RSV A/B) before vaccination and at each applicable postvaccination blood sampling time point; RSV NT fold rise from before vaccination to each applicable postvaccination blood sampling time point for RSV A, RSV B, and RSV A/B (refer to [Section 3.1.4.1](#) for derivation of fold rise and RSV A/B assay values).
- **Intercurrent events:** Similar to [Section 2.1.1.1](#), all data after intercurrent events 1, 2, and 3, as well as all data at intercurrent event 4, if collected, will be excluded. Major protocol violations will be determined by clinical review (through the data handling memo).
- **Population-level summary:** The group means measured as GMTs and GMFRs for the 2 treatment groups separately.

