1.3. Schedule of Activities

The SoA table provides an overview of the protocol visits and procedures. Refer to Study Assessments and Procedures in [Section 8](#) for detailed information on each procedure and assessment required for compliance with the protocol. The investigator may schedule visits (unplanned visits) in addition to those listed in the SoA table, to conduct evaluations or assessments required in order to protect the well-being of the participant.

Schedule of Activities

Visit Identifier	Visit 1	Visit 2	Visit 3
Visit Description	Day 1 Vaccination 1	Month 1 Vaccination 2	Month 2
Visit Window	-	28-35 Days after Visit 1	28-35 Days after Visit 2
Obtain informed consent	X		
Obtain participant number via IRT	X		
Obtain demography and significant medical history data	X		
Record current/former tobacco usage	X		
Perform clinical assessment (and physical examination if deemed necessary)	X		
Record nonstudy vaccinations, review concomitant medication use	X	X	X
Review inclusion and exclusion criteria and confirm eligibility	X		
Obtain participant's temperature	X	X	
Review temporary delay criteria	X	X	
Obtain blood sample for antibody assessment (~30 mL)	X ^a	X ^a	X
Obtain randomization number and kit assignment from IRT	X		
Explain/review participant communication methods, assist with downloading the e-diary application, or issue provisioned e-diary device, if required.	X		
Provide e-diary training, issue thermometer and measuring device	X	X ^b	
Administer SIIV in right deltoid muscle	X		
Administer study intervention in left deltoid muscle	X	X	
Discuss contraceptive use (as appropriate)	X	X	
Issue ECC and explain its purpose and use	X	X ^b	
Postvaccination observation (30 minutes) and immediate reaction assessment	X	X	
Review e-diary data,(daily during the 7 days after vaccination)	X	X	
Review e-diary for ongoing events and stop dates, collect e-diary ^c		X	X
Record AEs/SAEs and stop dates for previously reported events.	X	X	X

- a. Blood sample must be collected before vaccination.
- b. Issue replacement thermometer, measuring device, and ECC, only if required
- c. Collect provisioned e-diaries at Visit 3 only.

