- Following vaccination, the investigator or appropriately qualified designee reviews the daily e-diary data online to evaluate participant compliance and as part of the ongoing safety review.

8.9.2. Visit 2 – Vaccination 2 (Clinic, 28 to 35 Days After Visit 1)

- Record details of any nonstudy vaccinations and concomitant medications as described in [Section 6.10.4](#).
- Record AEs and SAEs as described in [Section 8.3.1](#) Obtain and record any missing AE stop dates.
- Review the participant's e-diary data. Collect stop dates of any ed diary events ongoing on the last day that the e-diary was completed and record stop dates in the CRF.
- Obtain the participant's body temperature.
- Ensure that none of the temporary delay criteria are met (see [Section 5.5](#)).
- Prior to Vaccination 2, collect a blood sample of approximately 30 mL for antibody assessment.
- Qualified site staff member(s) will administer a single dose of study intervention into the deltoid muscle of the **LEFT** arm.
- Observe the participant for any acute reactions for at least 30 minutes after study intervention administration. Record any acute reactions, including the time of onset, in the participant's source documents, on the AE page of the CRF, and on the Vaccine SAE Reporting Form if applicable.
- Discuss contraceptive use (where applicable) and as described in [Section 10.3.4](#).

- Confirm that the e-diary is set up for Vaccination 2 and review instructions, if necessary. Ask the participant to complete the e-diary from Day 1 to Day 7, with Day 1 being the day of Vaccination 2. Provide thermometer, measuring device, or ECC, if needed.
- Ask the participant to contact the site staff or investigator immediately if he/she experiences any of the following reactions from Day 1 to Day 7 to determine if an unscheduled reactogenicity visit is required ([Section 8.9.4](#))
- Fever $\geq 39.0^{\circ}\text{C}$ ($\geq 102.1^{\circ}\text{F}$).
- Redness or swelling at the **LEFT** injection site measuring >20 measuring device units (greater than 10 cm).
- Severe pain at the **LEFT** injection site.
- Any severe systemic event.
- Any emergency room attendance or hospitalization
- Advise the participant that study staff may make contact to obtain additional information on events entered in the e-diary.
- Advise the participant to inform the study staff of any AEs and SAEs that occur for the duration of the study as described in [Section 8.3.1](#).

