- Request that the participant brings the completed e-diary to the next visit.
- Schedule an appointment for the participant to return for the final study visit.
- Complete the source documents.
- The investigator or an authorized designee completes the CRFs and the dispenser/administrator completes the study intervention accountability records.
- Following vaccination, the investigator or appropriately qualified designee reviews the daily e-diary data online to evaluate participant compliance and as part of the ongoing safety review.

8.9.3. Visit 3 Follow-Up After Vaccination 2 (Clinic, 28 to 35 Days After Visit 2)

- Obtain details of any nonstudy vaccinations as described in [Section 6.10](#).
- Review concomitant medication use as described in [Section 6.10](#).
- Collect a blood sample of approximately 30 mL for antibody assessment.

- Review the participant's e-diary data. Collect stop dates of any ed diary events ongoing on the last day that the e-diary was completed and record stop dates in the CRF. Collect the sponsor-provisioned e-diary.
- Record AEs and SAEs as described in [Section 8.3.1](#). Obtain and record any missing AE stop dates.
- Complete the source documents.
- The investigator or an authorized designee completes the CRF.

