3.1.4. Secondary Immunogenicity Endpoints

3.1.4.1. RSV A– and RSV B–Neutralizing Antibody Titers

RSV A– and RSV B–neutralizing antibody titers will be determined at each visit.

Titers above the LLOQ are considered accurate and their quantitated values will be reported. Refer to [Section 5.3.2](#) for LLOQ details. Titers below the corresponding LLOQ, or denoted as BLQ, will be set to $0.5 \times \text{LLOQ}$ for analysis. Missing assay results will not be imputed.

RSV A and RSV B NTs at each blood sampling time point are included in the assay result data, thus no derivation is needed. The following variables will be derived for each participant:

1. RSV A/B at each blood sampling time point: This will be derived as the geometric mean of RSV A and RSV B NTs measured at each blood sampling time point.
2. RSV A, RSV B, and RSV A/B NT fold rise: This will be derived from before vaccination with RSVpreF to each visit after RSVpreF vaccination. The numerator is the postvaccination value and the denominator is the prevaccination value. For the coadministration group, assay results at Visit 1 will be used. For the sequential-administration group, assay results at Visit 2 will be used, if both Visit 1 and Visit 2 data are available; otherwise, the assay results at Visit 1 will be used, if only Visit 1 assay results are available.

When calculating a fold rise, if assay results are $< \text{LLOQ}$, the assay results will be converted to $0.5 \times \text{LLOQ}$, except when the prevaccination assay result is $< \text{LLOQ}$ while the postvaccination result is $\geq \text{LLOQ}$, in which case the prevaccination value will be set to LLOQ.

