6.2.1.1. Main Analysis

- Estimand strategy: Hypothetical approach ([Section 2.1.2.1](#)).

- Analysis set: Evaluable immunogenicity population ([Section 4](#)).
- Analysis methodology: 95% CIs of GMTs and GMFRs ([Section 5.2.2](#)).
- Intercurrent events and missing data: All data collected after or at intercurrent events will not be included; missing data will not be imputed.
- Descriptive statistics, including sample size (n), GMTs, GMFRs, and 95% CIs for GMTs and GMFRs will be presented for each vaccine group ([Section 5.2.2](#)).
- RCDCs for RSV A and RSV B will be plotted at 1 month after RSV vaccination, by vaccine group.

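### Read literally, the secondary RSV analysis applies the 1-month blood-draw window to every sample and so excludes all on-schedule coadministration Visit 3 results from its main GMT and GMFR tables

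*SAP*

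**What the plan says.** **The window.** SAP 2.1.1.1 defines intercurrent event 4 for the primary RSV estimand: "Blood was taken outside an acceptable window for immunogenicity evaluation (<25 days after RSVpreF administration or >49 days after RSVpreF administration". No visit is named. The primary variables contain only the 1-month sample (Visit 2 for coadministration, Visit 3 for sequential), so none is needed there.

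**Its reuse.** SAP 2.1.2.1 handles intercurrent events for the secondary RSV estimand by reference to 2.1.1.1 and says that "all data after intercurrent events 1, 2, and 3, as well as all data at intercurrent event 4, if collected, will be excluded". SAP 6.2.1.1 repeats this for the main secondary analysis: "All data collected after or at intercurrent events will not be included; missing data will not be imputed". Neither section gives a window for any later sample.

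**What the secondary analysis covers.** Its variables are neutralizing titers and fold rises for RSV A, RSV B and RSV A/B at each applicable time point after vaccination. On fold rise, SAP 3.1.4.1 says: "This will be derived from before vaccination with RSVpreF to each visit after RSVpreF vaccination". Protocol 8.1.2.2 has sera from all three visits assayed for RSV A and RSV B.

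**Timing.** The treatment condition in SAP 2.1.2.1 is "RSVpreF administered at Visit 1 in the coadministration group and RSVpreF administered at the Month 1 visit (Visit 2) in the sequential-administration group". The Protocol section headings put Visit 2 at "Clinic, 28 to 35 Days After Visit 1" (8.9.2) and Visit 3 at "Clinic, 28 to 35 Days After Visit 2" (8.9.3). The Schedule of Activities agrees.

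**The concern.** A window built for one sample has been carried into an analysis that uses two in the coadministration group. Visit 3 in that group is about two months after RSVpreF, beyond the 49-day limit even when the participant attends exactly as planned.

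The secondary estimand targets the setting in which participants keep to the schedule, yet its exclusion rule treats a draw made on schedule as an intercurrent event. The parallel SIIV estimand (SAP 2.1.2.2) has no such problem, because its only postvaccination sample is the 1-month one.

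At stake is the main-analysis summary of the trial's only RSV titers later than 1 month after RSVpreF. The sequential group has just one visit after RSVpreF, so no other sample can supply it. A programmer following the text would leave the time point empty. One who kept the data would be departing from two explicit statements, with no written rule for which draws count.

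**Working it through.** The documents give no figure for the timing of this sample, so there is none to reproduce. The check is arithmetic on the visit windows.

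**Inputs**
- Visit 1 to Visit 2: 28 to 35 days (Protocol 1.3, 8.9.2).
- Visit 2 to Visit 3: 28 to 35 days (Protocol 1.3, 8.9.3).
- RSVpreF given at Visit 1 (coadministration) or Visit 2 (sequential).
- Event 4: draw before day 25 or after day 49, counted from RSVpreF (SAP 2.1.1.1).
- Planned evaluable number: 650 per group (Protocol 9.5).

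**Formula.** Days from RSVpreF to the coadministration Visit 3 draw = (Visit 2 − Visit 1) + (Visit 3 − Visit 2).

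**Results for coadministration Visit 3**

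| Assumed gaps | Range in days | Combinations inside 25–49 |
|---|---|---|
| Both on the protocol schedule (28–35) | 28+28=56 to 35+35=70 | 0 of 8×8=64 |
| Visit 2 at the evaluable limits (25–49), Visit 3 on schedule | 25+28=53 to 49+35=84 | 0 of 25×8=200 |
| 25–49 for both gaps | 25+25=50 to 49+49=98 | 0 of 25×25=625 |

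The third row is an assumption. SAP Section 4 sets 25–49 days between Visits 2 and 3 for the sequential group only.

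**How far outside.** On schedule, the draw is 56−49=7 to 70−49=21 days past the limit. To be kept, it would have to be taken at most 49−28=21 days after an on-schedule Visit 2, or at most 49−25=24 days after a Visit 2 on day 25. Both are earlier than the 28-day start of the Visit 3 window.

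**Samples not touched.** Coadministration Visit 2 and sequential Visit 3 both fall 28 to 35 days after RSVpreF, inside 25–49.

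**What is lost.** Three titers (RSV A, RSV B, RSV A/B) times two summaries (GMT, GMFR) gives 3×2=6 main-analysis summaries, in one group at one visit. With event 4 limited to the 1-month sample, all 64 on-schedule combinations are kept instead of none.

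**The case against.** The strongest reply is that the plan never meant to exclude these samples.

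- The secondary estimand assumes the schedule is followed, so an on-schedule draw is hard to call an intercurrent event.
- SAP 2.1.2.1 describes its handling only as similar to 2.1.1.1 and does not restate the days.
- SAP Section 4 ties the 25–49 day window to the 1-month draw.
- SAP 3.1.4.1 plainly expects fold rises at Visit 3.
- If event 4 were tested on every sample, even the draws before RSVpreF would arguably fail the 25-day lower limit, which nobody intends.

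This makes a drafting carry-over likely, and a programmer may well keep the data. It does not remove the problem. The Section 4 window decides which participants enter the evaluable population. It does not cancel an exclusion of samples stated in 2.1.2.1 and again in 6.2.1.1. The supposed intention has to be inferred against the text.

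The reply does succeed against stronger readings that a reader might infer:

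- *The 2-month GMT and GMFR are lost altogether.* They are not. SAP 2.1.3 and 6.2.1.2 plan the same summaries in the mITT population under treatment policy, which keeps these samples.
- *The main and mITT tables would contradict each other.* They address different estimands. An empty cell beside a filled one is not a conflicting result.
- *A between-group comparison is lost.* The sequential group has no 2-month sample, so none was available.

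**Conclusion.** The point holds as a rule that gives the wrong result when followed as written. Under SAP 2.1.2.1 and 6.2.1.1, every on-schedule coadministration Visit 3 sample (56 to 70 days after RSVpreF) drops out of the main secondary GMT and GMFR analysis, although SAP 3.1.4.1 plans for it.

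The size is up to about 650 participants. That is an upper bound: it is the planned evaluable number, it assumes all of them attend Visit 3, and the evaluable RSV definition does not require a Visit 3 draw in the coadministration group.

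The reach is limited. The secondary objective is descriptive. A reader might infer some effect on the main conclusions, but the documents do not support that: the noninferiority tests and their power use only 1-month samples, and the 1-month secondary results also stand. The conclusion rests on the literal wording. If the sponsor intended the window for the 1-month sample only, the text still needs to say so.

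**What to change.** In SAP 2.1.2.1, state that event 4 (a draw outside 25 to 49 days after RSVpreF) applies only to the 1-month post-RSVpreF sample, and that coadministration Visit 3 results are kept in the main secondary analysis. Repeat the limit in SAP 6.2.1.1. This matches the Section 4 population definition, which needs no change.

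Optionally, give the coadministration Visit 3 sample its own window. Express it in days after RSVpreF, since counting from Visit 2 would anchor it to the placebo injection and, with 25 to 49 days for each gap, admit draws from day 50 to day 98. The window should contain days 56 to 70, and a draw outside it should remove that time point only.

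The cost is about one sentence in each section and a programming flag, with no new data. Settle it before unblinding, when SAP Section 4 already requires population classifications to be complete, so that the choice cannot look driven by results.
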